Cognitive Behavioral Therapy for Insomnia
for Veterans with History of TBI

NCT02658669

September 26, 2023

Study Protocol

Pre-study screening (15-30 minutes): Initial screening for interest and eligibility will take place in person or via telephone. Veterans will be given an overview of the study and, after providing verbal consent, will be screened with a questionnaire covering the major inclusion/exclusion criteria. Veterans who were not excluded based on the phone screening and who express interest in participating in the study will be invited to come to the VASDHS for continued evaluation of eligibility for participation in the study.

Baseline-Intake (2 hours): During the intake appointment, Veterans will first provide written informed consent and HIPAA consent and then be screened for sleep disorders using the Duke Structured Interview for Sleep Disorders. At this appointment, we will further confirm/document history of mild traumatic brain injury (mTBI) by noting number of mTBI events, type (blast/blunt/both), and duration of LOC and PTA for each event. At this visit all Veterans will be assessed on a battery of self-report questionnaires selected to evaluate global areas of functioning including sleep, fatigue, mood, PTSD, pain, post-concussive symptoms, and quality of life (see Table 2). We will also administer a neuropsychological assessment battery consisting of standardized measures with strong psychometric properties covering cognitive functions often impacted by mTBI, sleep disturbance, and/or depression. As part of this battery the Word Memory Test⁴⁶ (WMT) will be delivered to assess validity of neuropsychological results. Neuropsychological data of Veterans who fail effort testing will not be included in subsequent moderator analyses of impact of cognitive functioning on treatment outcomes. All assessments will be administered by a trained research assistant. At the conclusion of this appointment, Veterans will be given a sleep diary to complete for 7 days to prospectively record sleep measures (e.g., "lights out," time to fall asleep, time spent awake during the night, total sleep time, and "lights on"). After the baseline evaluation phase is completed, Veterans will be randomized into one of two treatment conditions (CBT-I or Sleep Education control).

Cognitive-Behavioral Therapy for Insomnia (CBT-I: 50-minute sessions): CBT-I treatments will be randomly assigned and will be conducted utilizing the VA Roll-out treatment manual. The standard approach to treatment involves 6 weekly sessions, and addresses several important concepts, including the underlying causes of insomnia, sleep restriction and stimulus control techniques, relaxation training, and relapse prevention. A significant emphasis is placed on using a case formulation to inform the treatment, and we will do that here, especially as it applies to how the Veteran's experience with mTBI informs the formulation. The session-by-session details are presented in Table 1 below.

Table 1. VA ROLL-OUT CBT-I TREATMENT PROTOCOL

Session	Content	Homework	Measures / Handouts
1	Comprehensive assessment Goal setting Case conceptualization	Complete sleep diary	Case conceptualization form Sleep diary Insomnia Severity Index (ISI)
2	Review sleep diary Provide sleep education tailored to patient Introduce Stimulus Control (SC)* and Sleep Restriction Therapy (SRT)** guidelines and rationale anchored in sleep regulation Use cognitive therapy as needed Emphasize most relevant components and add components based on case conceptualization	Complete sleep diary Follow recommended times for getting into and out of bed Follow other relevant guidelines	Sleep diary ISI "A Guide to Overcoming Your Insomnia" Other relevant worksheets
3	Review sleep diary and adherence; Discuss adherence in relation to progress Modify Time in Bed (TIB) based on SRT Use cognitive therapy as needed Introduce relaxation when needed (unless already introduced in Session 2)	Complete sleep diary Follow recommended times for getting into and out of bed Follow other relevant guidelines (including relaxation home practice)	Sleep Need Questionnaire Sleep diary ISI Other relevant worksheets

4 & 5	Review sleep diary and adherence Discuss adherence in relation to progress Modify TIB based on SRT rules Use cognitive therapy as needed	Complete sleep diary Follow recommended times for getting into and out of bed Follow other relevant guidelines	Sleep Need Questionnaire Sleep diary ISI Other relevant worksheets
6	Review sleep diary and adherence Modify TIB based on SRT rules Develop continued care plan Develop a relapse prevention plan	Follow continued care and relapse prevention plans	Action Plan for Addressing Insomnia in the Future Sleep Need Questionnaire ISI

*Sleep restriction therapy reduces nocturnal sleep disturbance primarily by restricting the time allotted for sleep each night so that, eventually, the time spent in bed closely matches the individual's presumed sleep requirement. This treatment typically begins by calculating the individual's average total sleep time from the sleep diary. An initial time-in-bed prescription is typically set at the total sleep time, however, is usually not set below 5 hours per night. On subsequent sessions the time in bed is titrated up or down in 20 to 30 minutes depending on sleep performance (sleep efficiency scores) over the past week.

**Stimulus control therapy is based on the assumption that both the timing (bedtime) and sleep setting (bed/bedroom) are associated with repeated unsuccessful sleep attempts and, over time, become conditioned cues for arousal that perpetuate insomnia. As a result, the goal of this treatment is to re-associate the bed and bedroom with successful sleep attempts. In practice, this therapy requires instructing the patient to: (a) go to bed only when sleepy; (b) establish a standard wake-up time; (c) get out of bed whenever awake for long periods; (d) avoid reading, watching TV, eating, worrying and other sleep-incompatible behaviors in the bed/bedroom; and (e) refrain from daytime napping.

Sleep Education Control Condition (50 minute sessions): The sleep education control condition used in this study is matched for number of sessions and length of sessions, however the content is modified to exclude the active components of standard CBT-I treatment. The sleep education control sessions focus on review of sleep diaries, providing information on relationship between sleep disturbance and mTBI, presentation of sleep hygiene education, and reviewing daily stressors that may impact sleep (see Table 2 below).

Table 2. SLEEP EDUCATION CONTROL CONDITION PROTOCOL

Session	Content	Homework	Measures / Handouts
1	Veteran check-in Provide information on relationship between sleep disturbance and TBI Description of sleep management	Complete sleep diary	Sleep diary Insomnia Severity Index (ISI)
2	Veteran check-in Review sleep diary Present sleep hygiene education	Complete sleep diary	Sleep diary ISI
3	Veteran check-in Review sleep diary Present sleep hygiene education	Complete sleep diary Change one aspect related to sleep hygiene	Sleep diary ISI
4	Veteran check-in Review sleep diary Review stressors related to sleep	Complete sleep diary Change one aspect related to sleep hygiene	Sleep diary ISI
5	Veteran check-in Review sleep diary mTBI education	Complete sleep diary Change one aspect related to sleep hygiene	Sleep diary ISI
6	Veteran check-in Review sleep diary Review techniques learned and strategies used over past five weeks of sleep education sessions	Complete sleep diary	Sleep diary ISI

Post-treatment Assessment: In the week following completion of the final treatment module, Veterans will be given a sleep diary to fill out for 7 days to prospectively assess sleep at post-treatment. At the end of the post-treatment evaluation week Veterans will return to the VASDHS to turn in the diary and will at this time be administered the same battery of clinical assessments originally given during the baseline evaluation visit.

1-Month Follow-up: 30 days following completion of post-treatment assessment Veterans will be contacted and asked to participate in a 1-week follow-up assessment of their sleep and functioning. For follow-up Veterans will be given a sleep diary to fill out for 7 days to prospectively assess sleep at post-treatment. At the end of the sleep tracking week Veterans will return to the VASDHS to turn in the diary and will at this time be administered the same battery of clinical assessments originally given during the baseline and post-treatment evaluation visits. At the conclusion of this session the Veteran will have completed participation in the study.

Statistical Analysis

Specific Aim 1: To determine the efficacy of CBT-I relative to a Sleep Education control in Veterans with insomnia following mTBI.

Hypothesis 1b: Veterans treated with CBT-I will report significant improvement on secondary outcome measures of depression, PTSD, and global functioning and disability when compared to Veterans treated with Sleep Education. Analyses of this data will be conducted using the Random Regression Model for assessments conducted at baseline, mid-treatment (treatment Session 3), and at post-treatment using a similar methodology as described for hypothesis 1a. Bonferroni adjusted alphas will be used.

Independent variables: Treatment group (CBT-I versus Sleep Education control) and Time (Baseline, Mid-treatment [Session 3], Post-treatment).

Dependent variables: Depression (PHQ-9), PTSD (PCL-S), and global functioning and disability (World Health Organization Disability Assessment Schedule 2 [WHODAS-2]).

Specific Aim 2: Examine sleep efficiency as a mediator of distal effects of CBT-I on symptoms of comorbid depression and PTSD, and global functioning and disability.

Hypothesis 2: Veterans demonstrating improvement in sleep efficiencies will also show improvements in comorbid depression, PTSD, and global functioning and disability. The dependent or outcome measures will be evaluated throughout the study and will be used as repeated measures for all the available time points. For this hypothesis, we will use the same mixed model procedure identified in Hypothesis 1a and 1b. To test for mediation, we will utilize the analytic strategy described by Krull and MacKinnon^{67,68}. In this approach, four conditions must be met: a) a significant relationship between the independent variable (i.e., intervention condition) and the dependent variable, b) a significant relationship between the independent variable (i.e., intervention) and the proposed mediator (sleep efficiency), c) a significant relationship between the mediator (sleep efficiency) and the outcome measures, and d) the relationship between the independent variable (intervention) and outcome measures must be significantly lower after controlling for the mediator. To test for significant mediation, we will conduct a Sobel test⁶⁹. We will also use the formula provided by MacKinnon and Dwyer⁷⁰ to determine the percentage of the intervention condition to primary outcome path that was accounted for by change in the mediator.

Independent variables: Treatment group (CBT-I versus Sleep Education control)

Dependent variables: Depression (PHQ-9), PTSD (PCL-S), and global functioning and disability (World Health Organization Disability Assessment Schedule 2 [WHODAS-2]).

Mediator: Sleep efficiency.

Specific Aim 3: Examine the effects moderator variables on CBT-I treatment outcomes

Hypothesis 3: We anticipate that several post-concussive factors such as depression, PTSD, and physical pain may moderate treatment outcomes whereas other factors such as global functioning and disability, neuropsychological functioning, and medication use will not moderate treatment outcomes. The rationale for this hypothesis comes from published work suggesting psychopathology and pain may play a significant role in maintenance of post-concussive symptoms (such as sleep disturbance) in patients with history of TBI²¹ thereby potentially impacting CBT-I treatment outcomes. Conversely, factors such as neuropsychological functioning, disability, and medication use have not been previously demonstrated to impact and/or moderate CBT-I treatment outcomes in a significant manner. These positional moderators will be explored by adding one outcome at a time to the Random Regression Model.

Independent variable: Treatment group (CBT-I versus Sleep Education control).

Dependent variable: Sleep efficiency.

Moderators: Depression (PHQ-9), PTSD (PCL-S), global functioning and disability (World Health Organization Disability Assessment Schedule 2 [WHODAS-2]), pain (BPI), neuropsychological functioning, and medication use (e.g., hypnotics, SSRIs).

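### Hypothesis 3 predicts that three factors will not moderate the CBT-I effect, but names no interaction term, margin or confidence-interval criterion that could support a claim of absence

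*Combined protocol and SAP*

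**What the plan says.** Under Statistical Analysis, Specific Aim 3, Hypothesis 3 expects that depression, PTSD and pain may moderate outcome, "whereas other factors such as global functioning and disability, neuropsychological functioning, and medication use will not moderate treatment outcomes". The reason given for the second group is that these factors "have not been previously demonstrated to impact and/or moderate CBT-I treatment outcomes in a significant manner".

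The outcome is given as "Dependent variable: Sleep efficiency". The moderators are PHQ-9, PCL-S, WHODAS-2, "pain (BPI), neuropsychological functioning, and medication use (e.g., hypnotics, SSRIs").

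One sentence describes the analysis: "These positional moderators will be explored by adding one outcome at a time to the Random Regression Model". The model it refers to is set out under Hypothesis 1a. It has a random intercept, a random time effect, and fixed effects for group and group-by-time.

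For Hypothesis 3 the plan gives no interaction term, alpha, smallest moderator effect of interest, equivalence margin, interval criterion or rule for describing a non-significant result. It gives no sample size or power for any aim.

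**The concern.** Half of Hypothesis 3 is a claim of absence. Such a claim needs an estimate of how much the CBT-I benefit varies with the factor, and an interval narrow enough to exclude variation that would matter. The plan asks for neither.

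The method sentence also stops short of a moderator analysis. Read literally, adding a factor to a model with group and group-by-time effects shows whether the factor predicts sleep efficiency. Whether it changes the benefit of CBT-I over Sleep Education is carried by a moderator-by-treatment-by-time term, which is not written.

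With no other criterion, a p-value above 0.05 is the only apparent way to judge the prediction. The stated rationale already reasons from a lack of earlier significant findings to an expectation of no moderation. At stake is a possible conclusion that CBT-I benefit does not depend on cognition, disability or medication, when the data might also fit a material dependence.

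**Working it through.** The plan has no figure to reproduce, so what follows is an illustration on stated assumptions.

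**Inputs**
- From the plan: two randomised arms; sleep efficiency as outcome; six listed moderators, each entered singly.
- Assumed: 1:1 allocation, two-sided alpha 0.05, and 80% or 90% power for the main effect D.
- Simplification: the treatment effect is treated as a single between-group contrast.

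**Main effect.** Noncentrality is D/SE = 1.96 + 0.84 = 2.80 at 80% power, and 1.96 + 1.28 = 3.24 at 90%.

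**Moderator split at the median, halves differing by D.** The SE of the interaction is SE/√(0.5 × 0.5) = 2 SE, so the noncentrality is halved.
- 80%: Φ(2.80/2 − 1.96) = Φ(−0.56) = 0.288, missed 71%.
- 90%: Φ(3.24/2 − 1.96) = Φ(−0.34) = 0.367, missed 63%.

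**Normal score kept continuous, linear moderation, median halves still differing by D.** The means of the two halves of a normal score are 2√(2/π) = 1.596 SD apart, so the slope is D/1.596 = 0.627D per SD. The SE of that slope equals the main-effect SE.
- 80%: 0.627 × 2.80 = 1.756; Φ(1.756 − 1.96) = 0.42, missed 58%.
- 90%: 0.627 × 3.24 = 2.031; Φ(2.031 − 1.96) = 0.53, missed 47%.

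**Halves differing by 2D (one gains nothing, the other 2D), median split.** Noncentrality is 2 × 2.80/2 = 2.80, or 3.24. Power is 80% or 90%, so the difference is missed 20% or 10% of the time.

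**Width of the 95% CI at 80% main-effect power.**
- Median split: 1.96 × 2/2.80 = 1.40D either side.
- Continuous: 1.96/2.80 = 0.70D per SD either side.
- With a median split, an interaction estimate of zero excludes 2D but not D. A non-significant estimate leaves 2D inside the interval only if it exceeds 2D − 1.40D = 0.60D.

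**What showing absence would take.** Take two one-sided 5% tests, a balanced binary moderator, a true difference of zero and 80% power. Total N = 16 × ((1.645 + 1.282)/margin)². A margin of 0.5 SD needs 549. For comparison, a main effect of 0.5 SD at 80% power needs 2 × 63 = 126 in total, from 2 × (2.80/0.5)² = 63 per arm. The plan gives no margin, so 0.5 SD is illustrative.

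**The case against.** The strongest reply is that Aim 3 is already tentative. Hypothesis 3 is an anticipation, the moderators are to be explored, and no primary or secondary result depends on them. That stands, and it limits the weight of the point. It does not supply a criterion for the three predicted nulls.

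A reader might infer any of four stronger things, which the documents do not support.
- *That the plan will read a null as confirmation.* It contains no interpretation rule for Aim 3. The risk is inferred from the wording of the hypothesis and the lack of any other criterion.
- *That the analysis has low power.* No sample size, alpha for this aim, or power is stated. Low power for an interaction of size D follows if the trial was sized at 80-90% for D, and that is an assumption. The median split is also not in the plan: the questionnaire moderators are scores, and keeping them continuous lowers the miss rate.
- *That the trial would probably overlook half its patients gaining nothing.* That is a 2D difference, and on these assumptions it would usually be detected.
- *That the effort-test rule tilts the result towards the predicted null.* The plan says "Neuropsychological data of Veterans who fail effort testing will not be included in subsequent moderator analyses". This reduces the sample by an unstated number, but it also removes invalid scores whose error could mask a real interaction. The net direction is not shown.

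The lack of a stated multiplicity adjustment for Hypothesis 3 is a separate matter. For an aim described as exploratory, requiring one would be a preference.

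**Conclusion.** The point holds. For disability, neuropsychological functioning and medication use, the plan predicts no moderation and provides no analysis that could support that prediction. The missing interaction term, margin and interval criterion can be seen in the text and depend on no assumption.

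The miss rates do depend on assumptions: 80-90% main-effect power, two-sided 0.05, equal allocation, and either a median split or a linear effect of a normal score. On those terms a moderator effect as large as the whole treatment effect would be missed roughly half to seven-tenths of the time (47-58% continuous, 63-71% split). Non-significance would therefore say little about effects of that size. It would be fairly informative about a difference of 2D. The consequence is confined to how a non-primary, exploratory aim may be interpreted.

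**What to change.** - Reword Hypothesis 3 so that no factor is predicted to have no effect.
- For each baseline factor, fit a moderator-by-treatment-by-time term with its lower-order terms, keeping scores continuous.
- Report the difference in CBT-I benefit at post-treatment, per SD or per category of the factor, with its 95% CI.
- State in advance that a non-significant interaction will be reported as moderation not shown, and not as evidence that the factor does not moderate.

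This needs no new patients or data, only revised wording and one table of interaction estimates. The downside is that the sponsor gives up the claim that CBT-I benefit is independent of cognition, disability and medication use. Keeping that claim would require a justified equivalence margin and a sample large enough to meet it.
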